6.6 Survival Follow-up

Subjects will be followed every 3 months from study drug discontinuation to monitor resolution or stabilization of any treatment-related medical events and obtain survival data. If possible, a MUGA scan, ECHO scan, or ECHO strain evaluation will be collected.

7. ASSESSMENT OF EFFICACY

7.1 Efficacy Parameters

7.1.1 Response Criteria

All subjects evaluable for efficacy will be assessed for response to treatment by using the recommendations of the International Working Group for standardization of response criteria, treatment outcomes, and reporting for therapeutic trials ([Cheson et al. 2003](#)). The primary efficacy variable is leukemia response rate, evaluated by the Investigator at the end of the cycle and at the EOS visit, based on bone marrow aspirate and peripheral blood collected at the end of the treatment cycle. A bone marrow (BM) aspirate (biopsy if there are no spicules present) should be repeated in 1 week if there is a question of residual leukemia in assessing efficacy based on an initial BM specimen.

An evaluation of response to therapy is one of the objectives of this study. Response criteria are described below:

Primary Endpoints:

1. Morphologic leukemia-free state
 - a. BM <5% blasts in an aspirate with spicules (a BM biopsy should be performed if spicules are absent)
 - b. No blasts with Auer rods or persistence of extramedullary disease
2. Complete remission:
 - a. Morphologic leukemia-free state in which
 - i. Subject is independent of transfusions
 - ii. Absolute neutrophil count of >1,000
 - iii. Platelets of $\geq 100,000$
3. Cytogenetic complete response – cytogenetics normal in those with previously abnormal cytogenetics
4. Cri and CRp: CR with incomplete blood count recovery meets all criteria for CR except for either neutropenia (<1,000; CRi) or thrombocytopenia (<100,000; CRp) but must include transfusion independence

Secondary Endpoints:

1. EFS: Time from enrollment until disease progression or death from any cause
2. OS: Time from enrollment until death from any cause
3. PR: All of the hematologic values for a CR, with normalization of blood counts, but with a decrease of at least 50% in the percentage of blasts to 5% to 25% in the bone marrow aspirate
4. Time to and duration of remission/response

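### Partial response stops at 5% blasts and ignores Auer rods, so an Auer-positive marrow at 20% can be PR while one cleared below 5% has no morphologic response category

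*Combined protocol and SAP*

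**What the plan says.** Section 7.1.1 (Response Criteria) lists the categories, and the Synopsis repeats them under Criteria for Evaluation (Efficacy).

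- **Morphologic leukemia-free state (MLFS):** "BM <5% blasts in an aspirate with spicules", together with "No blasts with Auer rods or persistence of extramedullary disease".
- **CR:** "Morphologic leukemia-free state in which" the subject is also transfusion-independent, with neutrophils above 1,000 and platelets of at least 100,000. CR therefore carries the Auer-rod and extramedullary condition.
- **CRi and CRp:** "CR with incomplete blood count recovery meets all criteria for CR except for either neutropenia" or thrombocytopenia. They carry the same condition.
- **Cytogenetic complete response:** "cytogenetics normal in those with previously abnormal cytogenetics". No blast or Auer-rod wording is attached.
- **PR (secondary endpoint 3):** "PR: All of the hematologic values for a CR, with normalization of blood counts", and "a decrease of at least 50% in the percentage of blasts to 5% to 25% in the bone marrow aspirate". Neither Auer rods nor extramedullary disease is mentioned.

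The same section says that subjects are "assessed for response to treatment by using the recommendations of the International Working Group", and then states that the criteria are set out below. It does not say which text prevails if the two differ.

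**The concern.** Response categories should be ordered: with everything else equal, a subject with fewer marrow blasts should not fall into a worse category. Here the lower limit of PR (5%) meets the upper limit of MLFS, but the two carry different side conditions. A subject who crosses 5% with residual Auer rods or persistent extramedullary disease leaves PR and is refused by every tier above it.

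PR is a named secondary endpoint and part of the antileukemic-activity objective in Section 2. Time to and duration of response depend on the same categories, so a subject in PR whose blasts fall further could lose response status by improving.

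The case can arise. Section 4 makes subjects with central nervous system involvement eligible, and Section 4.2 excludes such disease only when it is uncontrolled. Response is judged by the investigator at about seven centers, and no central response review is described, so sites could fill the gap differently. Sections 3.1 and 3.2 also make efficacy data part of the choice of recommended Phase 2 dose.

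**Working it through.** The plan states no figure for this point, so there is none to reproduce. The check applies the printed rules to example records.

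**Rules as printed** (x = post-treatment marrow blasts, B = baseline blasts)

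- MLFS: x < 5%, no Auer rods, no persistent extramedullary disease.
- CR: MLFS plus CR-level counts. CRi/CRp: CR with one count short.
- PR: CR-level counts, 5% ≤ x ≤ 25%, and x ≤ 0.5 × B.

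**Records with Auer rods present, neutrophils 1,500, platelets 120,000, no transfusions.** The last column applies the PR wording proposed under the fix.

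| Baseline | After | Fall | Printed list | With the fix |
|---|---|---|---|---|
| 60% | 20% | 66.7% | PR | PR |
| 60% | 5% | 91.7% | PR | PR |
| 60% | 4.9% | 91.8% | none | PR |
| 60% | 3% | 95.0% | none | PR |
| 40% | 20% | 50.0% | PR | PR |
| 39% | 20% | 48.7% | none | none |
| 30% | 20% | 33.3% | none | none |
| 6% | 4% | 33.3% | none | none |
| 3% | 3% | 0% | none | none |

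Four things follow.

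1. A 20% marrow is PR only if 20 ≤ 0.5 × B, that is B ≥ 40%, and only with CR-level counts. If counts have not recovered, neither the 20% nor the 3% Auer-positive marrow is a response.
2. Within those limits the order inverts: 20% is PR and 3% has no morphologic category. The switch comes between 5% and 4.9%.
3. Replacing Auer rods by persistent extramedullary disease gives the same results under the printed list.
4. Without either feature the printed list is ordered: at B = 60%, 20% is PR and 3% is CR.

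**Size.** One subject in the expansion is 1/21 = 4.8 percentage points. The documents give no frequency for the affected record, so the following is illustrative. Expected subjects = 21 × p × s, where p is the share clearing to under 5% with CR-level counts and s is the share of those keeping Auer rods or extramedullary disease. Assume s = 5% to 15%.

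- p = 1/16 = 6.25%, the complete remissions among AML subjects in the earlier Phase 1 study in Section 1.4 (other doses, a rough stand-in): 0.0625 × 0.05 to 0.0625 × 0.15 = 0.3 to 0.9 points, or 0.07 to 0.20 subjects of 21.
- p = 30%, a high value assumed with no support in the documents: 0.30 × 0.05 to 0.30 × 0.15 = 1.5 to 4.5 points, or 0.3 to 0.9 subjects of 21.

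The expected number reaches one only if p × s exceeds 1/21 = 4.8%. At s = 15% that needs p above 0.048/0.15, about 32%.

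**The case against.** **The cited external criteria may settle it.** The printed list could be a summary of the International Working Group text. That text is not reproduced, so whether it covers this case cannot be known here. This stands in part: a reader might infer that the cleared Auer-positive marrow is definitely scored as no response, and the documents support only that no printed morphologic category fits it. It does not remove the point, because the section says its criteria are described below and never says which source governs.

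**The repeat marrow handles it.** Section 7.1.1 asks for a second marrow in one week if residual leukemia is in question. That postpones the call. If the second marrow shows the same findings, there is still no category.

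**Cytogenetic complete response could apply.** A subject whose abnormal cytogenetics have become normal could literally meet that item. It supplies no morphologic tier and cannot help a subject whose cytogenetics were normal at the start.

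**Little depends on it.** Section 10 plans descriptive statistics only, with no response threshold or test, and few subjects are likely to be affected. That stands, and it makes this a low-priority clarification.

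**Conclusion.** The inversion is real under the printed definitions, within stated limits: CR-level counts, residual Auer rods or persistent extramedullary disease, and for the 20% example a baseline of at least 40%. It affects the PR endpoint and time to and duration of response. No error rate or sample size changes.

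Three stronger readings are tempting, and the documents do not support them.

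- A reader might infer that a combined CR-plus-PR rate is biased. No such rate is defined, and the components of leukemia response rate are not listed, so that variable is affected only if PR counts in it.
- A reader might infer that any 20% marrow with Auer rods is PR. At baselines of 30% or 39% it is not.
- A reader might infer a loss of several percentage points. That needs a clearance rate the documents do not give. Probably fewer than one subject of 21 is affected, though each one would move a 21-subject rate by 4.8 points.

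**What to change.** Make the same changes in Section 7.1.1 and the Synopsis.

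1. Keep the CR-level counts and reword the PR blast clause along these lines: *marrow blasts at least 50% below baseline, and either between 5% and 25%, or under 5% where morphologic leukemia-free state is not met only because blasts with Auer rods are present*. The 50% fall must apply to both branches. Section 4.1 sets no minimum marrow blast percentage, so a bare under-5% branch could score an unchanged 3% marrow as PR.
2. State whether persistent extramedullary disease is compatible with PR, and apply the answer identically above and below 5% blasts. If it is compatible, the under-5% branch must name it beside Auer rods. If it is not, PR must exclude it throughout. Either choice restores the order.
3. State that the printed list governs over the cited International Working Group text, or the reverse.

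Do not add a condition on new or increasing extramedullary disease: the Schedule of Events (Appendix A) has no serial assessment dedicated to it.

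The cost is one or two sentences in each place and the matching derivation code. Auer-rod status and persistence of extramedullary disease are already needed for MLFS. The choice should be made before response data are classified.

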7.2 Methods for Measuring Efficacy

Bone marrow aspirate/biopsy and peripheral blood specimens (complete blood count, differential, and platelet count) to document response will be collected at 15 to 35 days after the start of therapy. If cytogenetics were initially abnormal, include cytogenetics as part of the remission documentation. After documentation of remission, these procedures should be performed every cycle thereafter. In addition, flow cytometry analysis of peripheral blood may be utilized for response assessment.

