2. STUDY OBJECTIVES

The primary objective of this study is to evaluate the safety and identify the RP2D of liposomal annamycin for the treatment of subjects with AML that is refractory to or relapsed after standard induction therapy.

Secondary objectives:

1. Pharmacokinetics of annamycin and its metabolite, annamycinol
2. Preliminary assessment of the antileukemic activity of liposomal annamycin as second-line therapy for subjects with refractory or relapsed AML based on established response criteria, including complete response (CR), partial response (PR), event-free survival (EFS), overall survival (OS; Kaplan-Meier), and time to and duration of remission/response

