3.2 Dosing

The initial group of 3 subjects will be treated with a 2-hour intravenous infusion of 100-mg/m²/day (Dose Level 1) liposomal annamycin daily for 3 consecutive days followed by 18 days off study drug (i.e., 1 treatment cycle = 21 days). Provided that no subject experiences a DLT (defined in [Section 3.4](#)) during the induction treatment cycle through Day 28, the ensuing group of 3 subjects will receive 120-mg/m²/day (Dose Level 2) liposomal annamycin.

The liposomal annamycin dose levels planned for investigation are outlined in [Table 3](#). The starting dose is Dose Level 1.

Table 3: Liposomal Annamycin Dose Levels

[figure not shown]
Dose Level Designation	Liposomal Annamycin Dose (mg/m ² /day) × 3 days
-1	90
1	100
2	120

For each dosing cohort, if 1 of the 3 initial subjects experiences a DLT ([Section 3.4](#)), the cohort of subjects at that dose level will be expanded to 6 subjects ([Figure 1](#)). If at least 2 of the 6 subjects experience a DLT, then 3 subjects will be treated at a lower dose. If a DLT occurs in at least 2 out of 6 subjects at Dose Level 1, the next 3 subjects will be enrolled into Dose Level -1. The MTD is defined as the highest dose of liposomal annamycin at which fewer than 2 (of a cohort of up to 6) subjects experience a DLT. The RP2D is defined as the dose to be

explored in the expansion phase portion of the study, based on the aggregate data of safety and efficacy.

Figure 1: Schematic of Dosing Plan

Liposomal annamycin will be administered for a single induction cycle.

Abbreviations: DLT = dose-limiting toxicity; HSCT = hematopoietic stem cell transplantation.

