7. ECG

In addition to the weekly evaluations during the induction cycle, the following evaluations will be conducted at the end of the 3-week treatment cycle:

1. MUGA or ECHO scan or ECHO strain evaluation between Days 18 and 28. Cardiology consultation should be requested if any question arises about cardiac function. The MUGA scan should also be conducted at the Early Termination visit for subjects who are withdrawn prematurely.
2. Bone marrow aspirate and peripheral blood specimens (complete blood count, differential, and platelet count; flow cytometry is optional) between Days 15 and 35 to document response
3. Pregnancy test (with sensitivity of at least 50 mIU/mL) for women of childbearing potential on Day 21
4. Blood sample for cardiac biomarkers on Day 21

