^d CBC with differential and platelet count will be repeated if subject experiences a hematological toxicity that could be classified as a DLT after the first dose of the study drug.

^e Pregnancy test for women of childbearing potential within 72 hours prior to first dose of study drug and on Day 7 and Day 21

^f Within 2 weeks prior to the first dose of study drug

^g A final MUGA or ECHO scan or an ECHO strain evaluation will be conducted between the Day 18 and Day 28 visits or at the the End of Treatment visit if the subject is prematurely terminated.

^h For peripheral blood, include CBC, differential, and platelet count. In addition, flow cytometry analysis of peripheral blood may be utilized for measuring disease (optional). Bone marrow aspirate is sufficient if there are spicules present; if not, bone marrow biopsy is required (designated aspirate/biopsy below)

ⁱ CBC, blood chemistry, urinalysis, and ECGs should be repeated if screening was ≥ 14 days prior to first dose of study drug.

^j Bone marrow aspirate and peripheral blood (complete blood count, differential, and platelet count; flow cytometry is optional) within 15 days prior to the first dose of liposomal annamycin to document disease status. Bone marrow aspirate/biopsy 15 to 35 days after the start of therapy will be performed. If cytogenetics were initially abnormal, include cytogenetics as part of the remission documentation.

^k Blood samples for PK analysis collected at predose and at 0.25, 0.5, 1, 2, 4, 8, and 24 hours if clinically feasible and within a reasonable timeframe of the indicated times after the start of liposomal annamycin infusion on Day 1 and Day 3 for 3 subjects at each dose and 6 subjects at the RP2D who complete the

3 days of dosing. ECGs will also be collected for all subjects involved in pharmacokinetic analyses at predose and at 4 and 24 hours after dosing on Days 1 to 3, except for the 6 subjects at the RP2D who will have ECGs on Days 1 and 3 only. Documentation of concomitant medications affecting CYP enzymes will be obtained to ensure that these are a consideration in the evaluation of the pharmacokinetics of this drug.

^l PK/ECG collection timepoint of 24 hours after the start of the infusion on Days 1 and 3, per above, will occur on Day 2 (predose) and Day 4.

^m Blood sample for cardiac biomarkers (troponin-I and troponin-T) will be collected at predose and at the end of the infusion on Day 3.

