ⁿ Liposomal annamycin is administered as a daily 2-hour intravenous infusion for 3 consecutive days followed by 18 days off liposomal annamycin (i.e., 1 treatment cycle = 21 days) every 3 weeks. Subjects will be hospitalized for the full 3 days of liposomal annamycin administration.

^o Mouthwash per institution's guidelines and practices

^p Antiallergic premedication with diphenhydramine at a dose of 50 mg administered intravenously must be administered before each dose of liposomal annamycin.

^q A MUGA scan, ECHO scan, or ECHO strain will be collected at the Q3-month survival timepoint if possible.

**APPENDIX B: EASTERN COOPERATIVE ONCOLOGY GROUP PERFORMANCE
STATUS SCALE**

Grade	Details
0	Fully active, able to carry on all predisease performance without restriction
1	Restricted in physically strenuous activity but ambulatory and able to carry out work of a light of sedentary nature, e.g., light house work, office work
2	Ambulatory and capable of all self care but unable to carry out any work activities. Up and about more than 50% of waking hours
3	Capable of only limited selfcare, confined to bed or chair more than 50% of waking hours
4	Completely disabled. Cannot carry on any self care. Totally confined to bed or chair.
5	Dead

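### After the response assessment, neither the Day 42 visit nor the 3-monthly contact asks for relapse status or date, so duration of remission and late EFS events need not be dated

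*Combined protocol and SAP*

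**What the plan says.** Section 2 lists among the secondary efficacy measures "event-free survival (EFS), overall survival (OS; Kaplan-Meier), and time to and duration of remission/response". Section 7.1.1 repeats them as secondary endpoints and defines one of them: "EFS: Time from enrollment until disease progression or death from any cause". It gives no start, end or censoring rule for duration. Section 10 is descriptive, covers safety and pharmacokinetics, and does not mention these endpoints.

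On disease assessment:

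- **Response marrow.** Section 6.3.2 asks for marrow and peripheral blood, including a blood count, "between Days 15 and 35 to document response". Footnote j of Appendix A agrees: "Bone marrow aspirate/biopsy 15 to 35 days after the start of therapy will be performed". Section 7.1.1 adds that the marrow "should be repeated in 1 week if there is a question of residual leukemia". It has the investigator judge response at the end of the cycle and at the end-of-study (EOS) visit, from those specimens.
- **After remission.** Section 7.2: "After documentation of remission, these procedures should be performed every cycle thereafter".
- **Number of cycles.** Section 3.2, under Figure 1: "Liposomal annamycin will be administered for a single induction cycle". Footnote n of Appendix A has instead "18 days off liposomal annamycin (i.e., 1 treatment cycle = 21 days) every 3 weeks".
- **Day 42 visit (Section 6.5).** Physical examination, adverse events and concomitant medications.
- **3-monthly contact (Section 6.6).** Treatment-related events, survival data and, if possible, cardiac imaging.
- **Withdrawal (Section 4.3).** Disease progression is a listed reason, and reasons are recorded.

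**The concern.** Duration of remission needs two dates: when remission was documented and when it ended. The plan collects the first. For the second it relies on a rule tied to later treatment cycles, in a trial whose dosing section describes one cycle. The contacts that do continue after the cycle do not ask whether or when leukemia returned.

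Deaths are followed every 3 months, so OS and the death part of EFS are covered. At stake are duration of remission and the part of EFS that comes from late relapse in remitters and later progression in others. A censoring rule can be written at analysis, but a relapse date that was never requested may not be recoverable by then.

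**Working it through.** The documents give no precision, power or event figure for these endpoints. The check is therefore of the visit calendar and of what each contact collects. The Appendix A grid is broken in the available text, so visit contents come from Section 6 and the footnotes.

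**1. Calendar**

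- Response marrow: Days 15 to 35.
- Conditional repeat: 15 + 7 = Day 22 to 35 + 7 = Day 42.
- Follow-up visit: the cycle ends on Day 21, EOS is within 1 week and follow-up is 2 weeks later, so at latest 21 + 7 + 14 = Day 42. This reproduces the Day 42 column of Appendix A.
- End of adverse event documentation (Section 8.2): last dose on Day 3, 3 + 39 = Day 42.
- First 3-monthly contact, counted from the last dose and taking 3 months as 91 days (my assumption): 3 + 91 = about Day 94.

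**2. Marrows required after remission is documented**

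- Under Section 3.2 there is 1 cycle, so later cycles = 1 − 1 = 0, and the Section 7.2 rule requires 0 further marrows.
- Under footnote n, a 3-week rhythm from Day 1 would start cycles on Days 22, 43, 64 and 85. Days 43, 64 and 85 fall between Day 42 and about Day 94, where no visit is listed.

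So neither wording yields a usable schedule.

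**3. Gap to the next contact after Day 42**

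- From the response marrow: 94 − 35 = 59 to 94 − 15 = 79 days.
- From the conditional repeat: 94 − 42 = 52 to 94 − 22 = 72 days.

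The contact at the end of that gap names survival, not disease status.

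**4. What the later contacts could pick up indirectly**

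- Concomitant medications at Day 42 may reveal a next therapy started by then.
- Appendix A appears to mark adverse event monitoring at the 3-monthly contact, but Section 8.2 ends documentation at Day 42 and Section 6.6 confines later follow-up to treatment-related events. None of these names relapse.

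**5. Effect on the estimates**

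Take a subject whose remission is documented on Day d (15 to 35), who relapses after Day 42, whose relapse is not recorded, and who is alive at last contact.

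- *Counted event-free to last contact:* the relapse is lost and only death can be an event. For such subjects EFS time equals OS time, and EFS is biased upward.
- *Censored at the last planned disease assessment:* if that is the marrow on Day d, duration is censored at d − d = 0 days. If a repeat marrow follows and duration is dated from the first, it is 7 days. If the Day 42 visit were accepted as evidence of continuing remission, although it lists no blood count or marrow, it would be 42 − 35 = 7 to 42 − 15 = 27 days.

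The visible text does not say which convention applies.

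**The case against.** The strongest reply has four parts.

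- **The endpoints are secondary, and the analysis is descriptive in at most 12 + 21 = 33 subjects.** This stands. It limits the importance of the point, but a descriptive duration still needs an end date.
- **Section 7.1.1 already defines the EFS event.** This also stands: a reader might infer that the plan has no EFS event at all, and that would be wrong. What the visible text lacks is any mention of relapse as an event, a start and end for duration, and a censoring rule.
- **Progression is a recorded withdrawal reason, with no time limit.** True, so a relapse may well be written down. But Section 4.3 schedules no assessment after remission and requests no relapse date from subjects in survival follow-up.
- **The cited International Working Group recommendations may define relapse and duration, and Figure 1, whose abbreviations include stem cell transplantation, may show what follows response.** Neither can be seen here, and nothing is claimed about them. Cited definitions alone would not add a question to the Day 42 or 3-monthly contact.

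Three stronger readings are tempting but unsupported. One is that blood counts stop before the marrow: the response specimen includes a count and can fall as late as Day 35. Another is to project the remissions of 5 and 13 weeks reported in Section 1.4 onto this calendar. Those came from two subjects, one with ALL, both treated for more than one cycle at 210 to 350 mg/m²/day. Here one cycle is described, at levels of 90 to 120. The third is a percentage of relapses missed, for which the documents supply no basis.

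**Conclusion.** The point holds as a gap in data collection and definition for two secondary endpoints. With a single cycle, the plan requires no marrow after the one that documents remission. The next contact after Day 42 comes 52 to 79 days after the last planned marrow, and it does not name disease status. Followed as written, late relapses need not be dated. EFS then moves toward OS, or duration is censored within 0 to 27 days of its start, according to a convention that is not stated.

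This rests on the visible text, on the visit days in step 1, and on sites collecting no more than is asked. Sites may in practice report relapse, which would shrink the problem but leave ascertainment uneven across the roughly 7 centers. Deaths, early non-response and early progression are captured. The safety and RP2D objective and the response rate are unaffected. The change should be made, preferably before follow-up data accrue; it is not a reason to doubt the dose-finding part.

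**What to change.** 1. **Sections 6.5, 6.6 and Appendix A.** At the existing Day 42 and 3-monthly contacts, record relapse or progression status and its actual date, next anti-leukemia therapy and its date, and transplant date, all from routine-care records.
2. **Sections 3.2 and 7.2 and Appendix A footnote n.** Reconcile the wording on cycles. Which wording is intended is for the sponsor to say; the passages cannot all apply together.
3. **Sections 7.1.1 and 10.** State that relapse after remission is an EFS event, that duration runs from documented remission to relapse or death, and that subjects without an event are censored at the last date their disease status was known. If the cited recommendations already supply the definitions, say so explicitly.

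How to treat transplant or next therapy in the analysis is a choice for the sponsor; collecting the dates keeps it open.

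**Cost.** A few eCRF fields and three sentences of endpoint wording, with no added visit or marrow. Sites must obtain outside records, and routine-care dates are less precise than protocol-timed ones.
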